### **STUDY OBJECTIVES**

The goal of this proposal is to assess the efficacy of radiation segmentectomy in patients with very early and early HCC as per BCLC, who cannot undergo thermal ablation. Towards this goal, we will also explore 1) Time to Progression 2) Quantifying dose to target lesion 3) Safety and 4) Toxicity.

### **Primary end point:**

## The Impact of $^{90}\text{Yttrium}$ (Y90) Radiation Segmentectomy on Unresectable Hepatocellular Carcinoma

Tumor response: Assess tumor response according to mRECIST

### **Secondary end points:**

1. Time to Progression: The length of time from radiation segmentectomy until progression of disease based on mRECIST.
2. Assess toxicity resulting from Radiation Segmentectomy with Theraspheres

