**Secondary Endpoints:**

- Time to Progression (TTP): The length of time from radiation segmentectomy until progression of disease based on mRECIST based on investigator evaluations.
- Assess toxicity resulting from Radiation Segmentectomy with Theraspheres

**Trial Population:** Patients diagnosed with Hepatocellular Carcinoma as per AASLD guidelines and not eligible for surgical resection or thermal ablation.

**Number of Patients:** 30

**Study Duration:** 2 years accrual and 2 years follow-up for a total of 4 years duration.

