## Imaging Requirements

- MRI scans abdomen/pelvis; To assess disease extension and to determine liver volume measurement and identify hepatic vascular anatomy.
- Spiral CT Chest –performed with cuts of 10 mm or less in slice thickness contiguously in the axial plane. To assess extra-hepatic lesions according to the RECIST v 1.1.
- Hepatic angiography and 99mTC-MAA – selective celiac and superior mesenteric arteriograms are needed to evaluate the hepatic arterial anatomy for the whole liver, as well as evaluation of potential sources of extra-hepatic blood supply to tumors. Repeat 99mTC-MAA may be needed to estimate cumulative lung shunt or re-asses GI flow.
- SPECT imaging may be performed according to standard of care practices for clinical management but is not a study requirement.
- PET/CT for quantification of dose to target lesion, as well as dose to non-target liver.

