### Progression:

Definition of tumor progression is defined as:

- Radiological progression as defined by mRECIST
- Development of extra-hepatic disease beyond the limits defined in the eligibility criteria
- ECOG Performance Status  $\geq 2$

ECOG Performance Status

Score Characteristics

0 Asymptomatic and fully active

1 Symptomatic; fully ambulatory; restricted in physically strenuous activity

2 Symptomatic; ambulatory; capable of self-care; more than 50% of waking hours are spent out of bed.

3 Symptomatic; limited self-care; more than 50% of waking hours are spent in bed

4 Completely disabled; no self-care; bedridden.

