## The Impact of Yttrium (Y90) Radiation Segmentectomy on Unresectable Hepatocellular Carcinoma

- o Chest CT scan (12 months after treatment and 24 months after treatment)

Progression:

Definition of tumor progression is defined as:

- Radiological progression as defined by mRECIST
- Development of extra-hepatic disease beyond the limits defined in the eligibility criteria
- ECOG Performance Status  $\geq 2$

ECOG Performance Status

Score Characteristics

0 Asymptomatic and fully active

1 Symptomatic; fully ambulatory; restricted in physically strenuous activity

2 Symptomatic; ambulatory; capable of self-care; more than 50% of waking hours are spent out of bed.

3 Symptomatic; limited self-care; more than 50% of waking hours are spent in bed

4 Completely disabled; no self-care; bedridden

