# The Impact of $^{90}\text{Yttrium}$ (Y90) Radiation Segmentectomy on Unresectable Hepatocellular Carcinoma

## Progression:

Definition of tumor progression is defined as:

- Radiological progression as defined by mRECIST
- Development of extra-hepatic disease beyond the limits defined in the eligibility criteria
- ECOG Performance Status  $\geq 2$

ECOG Performance Status

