### Score Characteristics

0 Asymptomatic and fully active

1 Symptomatic; fully ambulatory; restricted in physically strenuous activity

2 Symptomatic; ambulatory; capable of self-care; more than 50% of waking hours are spent out of bed.

3 Symptomatic; limited self-care; more than 50% of waking hours are spent in bed

4 Completely disabled; no self-care; bedridden

\* Grades of Encephalopathy

Grade 1      Inverted sleep pattern; forgetfulness, agitation, irritability, apraxia

Grade 2      Lethargy; Disorientation for time or place, Subtle personality change; Asterixis, ataxia

Grade 3      Somnolence but rousability; Disorientation as regards place; Asterixis, hyperactive reflexes, Babinski signs, muscle rigidity

Grade 4      Coma (unresponsive to verbal or noxious stimuli)

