### c. Delivery of Y90:

- Radiation segmentectomy will be performed with Yttrium-90, whereby a high radiation dose is delivered to the tumor via radioactive microspheres infused through the hepatic artery. The radioactive microsphere delivery device used will be glass-based (TheraSphere; BTG, Ottawa, Ontario, Canada), in which Y is an integral constituent of the biocompatible glass matrix.
- Patients will be subsequently imaged the same day with PET-CT to quantify dose to target tissue, as well as dose to the non-target liver. This will be performed on a PET-CT system (Siemens).

Patients who consent to the procedure, but cannot proceed with treatment due to dose resulting in  $>30 \text{ Gy}$  to the lungs or inability to target feeding vessels  $\leq 2$  Couinaud segments will be regarded as treatment failures.

Termination of Participation in Study to include those subjects who did not pass Y90 mapping test, as well as those who have clinical deterioration of concurrent medical conditions and those who decide to terminate participation.

Patients will undergo routine clinical surveillance at 6 weeks post-Y90, 12 weeks post-Y90, and at 3 month intervals post-Y90 for 2 years post Y-90 during which time they will be evaluated by the physician assistant/nurse practitioner and attending physicians, with assessment of their clinical performance, active medical issues, and any toxicities, as graded by the NCI CTCAE version 4.03. Follow-up will be within 7 days of scheduled times post-treatment.

	Screening	Mapping	Y90 Treatment	6 wks post	12 wks post	6 mo post	9 mo	12 mo	15 mo	18 mo	24 mo	End of Study
Informed Consent	X											
Demographics	X											
Medical History	X											
Physical Exam	X											
ECOG	X	X	X	X	X	X	X	X	X	X	X	X
Child Pugh	X											
AFP	X	X		X	X	X	X	X	X	X	X	
Prior Treatment Hx	X											
Hematology	X	X		X	X	X	X	X	X	X	X	

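### Time to progression is defined by mRECIST, but the protocol's general definition of tumor progression also counts ECOG 2 or more, and nothing says which governs the endpoint

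*Combined protocol and SAP*

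**What the plan says.** **The endpoint.** The main text (Secondary end points) defines TTP as "The length of time from radiation segmentectomy until progression of disease based on mRECIST". The synopsis (Secondary Endpoints) has "The length of time from radiation segmentectomy until progression of disease based on mRECIST based on investigator evaluations". Both name mRECIST and nothing else as the criterion.

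**The general definition.** A Progression subsection appears three times: in the synopsis follow-up section, in the main Study Visits and Follow-up section, and under Data Collection. Each time it opens with "Definition of tumor progression is defined as" and lists three items: radiological progression by mRECIST, "Development of extra-hepatic disease beyond the limits defined in the eligibility criteria", and ECOG performance status of 2 or more. The accompanying scale describes ECOG 2 by function alone: "Symptomatic; ambulatory; capable of self-care; more than 50% of waking hours are spent out of bed". No cause is required.

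**Related text.** Imaging Requirements gives the purpose of chest CT as "To assess extra-hepatic lesions according to the RECIST v 1.1", a criterion that the TTP wording does not mention. The main Delivery of Y90 section ends participation for, among others, "those who have clinical deterioration of concurrent medical conditions and those who decide to terminate participation". Chest CT follow-up is set at each follow-up visit in the synopsis and under Data Collection. The main Study Visits and Follow-up section has "Chest CT scan (12 months after treatment and 24 months after treatment", and the schedule table also marks only those two post-treatment times.

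Neither the synopsis statistical plan nor the Statistical Analysis section mentions TTP.

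**The concern.** TTP is the only time-based efficacy endpoint in an open-label, single-arm study assessed by the investigators. If its event can be read in two ways, the same patients can yield different event counts and dates, and the choice could be made after the data are known.

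The ECOG item is the sharpest problem. A patient whose function declines because of a concurrent illness, with no viable tumor on MRI, meets the listed definition of tumor progression. Under the endpoint wording that patient has not progressed. The list also appears under Data Collection, so staff could reasonably record such a patient as progressed.

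**Working it through.** The plan gives no event count, power or analysis method for TTP, so there is no figure to reproduce. The check is a comparison of texts plus one calculation of dates.

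**1. The items side by side**

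| Event | Endpoint wording (synopsis and main text) | Progression list (three places) |
|---|---|---|
| mRECIST progression | Counts | Counts |
| Extra-hepatic disease | Not named; may be within mRECIST | Counts, as a separate item |
| ECOG 2 or more | Not named; not a radiological finding | Counts, with no cause required |

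The list does not mention TTP, and the TTP wording does not mention the list. No section ranks them or limits the list to another purpose.

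**2. Which items go beyond mRECIST**

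The protocol's account of mRECIST defines progressive disease by growth of viable target lesions, but it is headed as a brief summary. It does not mention new lesions at all, so its silence on extra-hepatic disease cannot show that such disease falls outside the full criteria. Performance status is different: it is a functional score, and the mRECIST summary is wholly about imaging. ECOG 2 or more is therefore the one clear addition.

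**3. Direction of the effect**

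Let R, X and E be a patient's times to mRECIST progression, extra-hepatic disease and ECOG 2 or more. Under the list, TTP = min(R, X, E), which is never later than R. Example: a patient reaches ECOG 2 at 6 months and has no radiological progression through 24 months. The list gives an event at 6 months. The endpoint wording gives no event, with censoring at 24 months if the patient stays in follow-up.

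**4. Size of the ECOG effect**

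Entry requires ECOG 0, so the item needs a two-level decline. The documents give no rate for this in any cohort, so the number of added events among the 30 patients cannot be derived.

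**5. Withdrawal**

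The termination rule concerns leaving the study, not classifying an event. It matters here because a patient with non-tumor decline may leave before any radiological progression. The plan does not say whether or when that patient's TTP is censored.

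**6. Dating of disease seen only on chest CT**

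- Frequent schedule (synopsis; Data Collection): 6 weeks, 12 weeks, then every 3 months to 2 years, i.e. 6, 9, 12, 15, 18, 21 and 24 months. That is 9 scans. The schedule table has no 21-month column; on its columns there would be 8. The delays below do not change.
- Sparse schedule (main Study Visits and Follow-up; schedule table): 12 and 24 months. That is 2 scans.
- Six weeks in months: 6 × 7 / 30.44 = 1.38.
- Disease visible at 6 weeks: dated 1.38 or 12 months. Largest difference 12 − 1.38 = 10.6 months.
- Disease first visible after the 12-month scan and by 15 months: dated 15 or 24 months. Difference 24 − 15 = 9 months.

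These are upper limits. They ignore the 7-day visit window and apply only if extra-hepatic disease counts toward TTP and is not seen on the abdomen/pelvis MRI, which is scheduled at every follow-up visit.

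**7. Primary endpoint**

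The sample size (30 patients, complete response 80% against 50%, stated power 91%) uses response only. Nothing above enters it.

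**The case against.** The best reply is that the endpoint has its own definition, stated twice and consistently, and that Response assessment also specifies mRECIST. The list sits in the visit and data-collection sections and never mentions TTP. On ordinary reading, endpoint-specific wording governs. That is plausible, and it is why the point is an unreconciled general definition rather than two rival statements of TTP. But the protocol does not say so, and the broader definition is repeated three times.

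Several stronger readings are tempting and are not supported:

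- A reader might infer that extra-hepatic disease is a second clear departure from mRECIST. The brief summary cannot establish that, for the reason in step 2 of the working.
- A reader might infer that the protocol expressly counts ECOG decline whatever its cause. It is silent on cause. The accurate statement is that no attribution to tumor is required.
- A reader might treat the termination rule as a third definition of the event. A patient can have an event and then leave; the rule raises a censoring question only.
- A reader might scale event counts from the background cohorts. These populations differ from the trial's, neither supplies an ECOG rate, and Table 3 is not safe to use: its median TTP of 13.6 months means fewer than half are progression-free at 24 months, so its 55% two-year figure cannot be a progression-free proportion.

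It is also fair that the chest CT conflict is a separate defect. A single TTP definition would not remove it. It is noted here because it affects the date of one kind of TTP event.

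**Conclusion.** The point holds and should be fixed. The mismatch between the endpoint wording and the progression list is certain from the text. ECOG 2 or more is its clear substance; extra-hepatic disease needs an explicit statement only because the documents do not settle whether mRECIST already covers it.

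If the list is applied, the bias is toward earlier TTP. Its size is unknown and may be small, given the two-level decline required from entry. The dating difference for disease seen only on chest CT is at most about 10.6 months; it rests on taking the two printed schedules at face value and dating events at the scan.

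A reader might infer that the trial's main conclusion is at risk. It is not: TTP is secondary and unpowered, and the complete-response endpoint and its power do not depend on it.

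**What to change.** 1. In both TTP statements, make the event radiological progression only: mRECIST, stating that new intrahepatic lesions and new extra-hepatic disease count. This keeps to the stated endpoint and removes the doubt about the brief summary.
2. In all three Progression subsections, state that ECOG 2 or more is not a TTP event, and report it separately.
3. State how patients who leave under the termination rule are censored in the TTP analysis.
4. Reconcile the chest CT timing between the synopsis and Data Collection on one side and the main Study Visits and Follow-up section and schedule table on the other. This review does not choose a schedule.

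Items 1 to 3 are wording changes, with no added patients or visits. The consequence of item 4 depends on which schedule the sponsor confirms. The small downside is that TTP may look longer than under the three-item list. Other censoring rules, for example at transplant, which the protocol permits, would still need to be stated.

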### **Response assessment:**

Response assessment will be performed with mRECIST 6 weeks post-radiation segmentectomy, 12 weeks post-radiation segmentectomy and every 3 months thereafter for a period of 2 years to correlate with data collection. Imaging will be performed within 7 days of scheduled visits.

## **DATA and METHODOLOGY**

This is a prospective, single arm study. Segmentectomy within the context of this protocol will be offered to patients with a single site of HCC  $\leq 3$  cm diameter who are not eligible for thermal ablation. Patients may, if otherwise qualified either before or after treatment, be included on the waiting list for LT.

### **Diagnosis**

The diagnosis of HCC will be established using updated AASLD criteria based on CT or MRI. Histological confirmation will be obtained in non-cirrhotic patients.

### **Inclusion Criteria:**

1. Age greater than 18 years, regardless of race or gender
2. Hepatocellular Carcinoma confirmed by histology for non-cirrhotic patients or non-invasive criteria according to AASLD for cirrhotic patients.
3. Child-Pugh class A or B7 without ascites
4. Single tumor nodule  $\leq 3$  cm with a maximum distance of 5 mm from either portal vein, hepatic vein, inferior vena cava, diaphragm, heart, stomach, bowel, liver capsule, gallbladder, bile duct.
5. No prior locoregional treatment or external beam therapy of current HCC (recurrent HCC after resection may be included)
6. No confirmed extrahepatic metastases
7. No evidence of macrovascular invasion
8. ECOG 0
9. Albumin  $\geq 3.0$  g/dL
10. PLT  $\geq 40 \times 10^3/\mu\text{L}$
11. WBC  $\geq 1.5 \times 10^3/\mu\text{L}$

## The Impact of Yttrium (Y90) Radiation Segmentectomy on Unresectable Hepatocellular Carcinoma

12. AST/ALT  $\leq$  5 times the upper limit of normal (U/L)
13. Creatinine  $\leq$  2.0 mg /dL
14. No indication for any possible curative treatment after multidisciplinary assessment (surgery, ablation). Unresectable parameters include platelets  $< 100 \times 10^3/\mu\text{L}$ , portal hypertension, Total Bilirubin  $> 1.0 \text{ mg/dL}$ , and comorbidities which exclude surgery agreed upon during the multidisciplinary meeting.
15. No contraindication to angiography or selective visceral catheterization
16. No history of severe allergy or intolerance to contrast agents, narcotics, sedatives.
17. Negative serum pregnancy test
18. Signed informed consent form

### **Exclusion Criteria:**

1. Inability to provide informed consent
2. Pregnancy
3. Metastatic disease outside of the liver
4. Macrovascular invasion
5. Child-Pugh class  $> \text{B7}$
6. Total Bilirubin  $> 2.0 \text{ mg/dL}$
7. Platelets  $< 40 \times 10^3 \text{ per mm}^3$
8. Encephalopathy\* (Defined below)
9. Refractory ascites
10. Greater than a single nodule  $> 3 \text{ cm}$

### **Study Visits and Follow-up**

#### Screening:

Images and test results obtained for clinical patient management and before signing of informed consent do not need to be repeated and may be used for screening assessment provided images were taken within 28 days. These evaluations will be the baseline values for patients in the trial.

#### Follow-up:

Patients will be followed within 6 weeks after treatment, 12 weeks after treatment and 3 months thereafter for a period of 2 years. Visits will occur within 7 days of scheduled appointments.

#### Visits include assessment of:

- o ECOG Performance Status assessment
- o Standard laboratory blood draw for CBC, differential, electrolytes, BUN, glucose, liver function test, coagulation panel, and  $\alpha$ -fetoprotein biomarker
- o Adverse event reporting
- o Abdomen/pelvis MRI (6 weeks after treatment, 12 weeks after treatment and 3 months thereafter for a period of 2 years)

## The Impact of Yttrium (Y90) Radiation Segmentectomy on Unresectable Hepatocellular Carcinoma

- o Chest CT scan (12 months after treatment and 24 months after treatment)

Progression:

Definition of tumor progression is defined as:

- Radiological progression as defined by mRECIST
- Development of extra-hepatic disease beyond the limits defined in the eligibility criteria
- ECOG Performance Status  $\geq 2$

ECOG Performance Status

Score Characteristics

0 Asymptomatic and fully active

1 Symptomatic; fully ambulatory; restricted in physically strenuous activity

2 Symptomatic; ambulatory; capable of self-care; more than 50% of waking hours are spent out of bed.

3 Symptomatic; limited self-care; more than 50% of waking hours are spent in bed

4 Completely disabled; no self-care; bedridden

## Data Collection

Patients will be interviewed and clinical information will be obtained at baseline, 6 weeks after treatment, 12 weeks after treatment and 3 months thereafter for a period of 2 years. Visits will occur within 7 days of scheduled appointments.

Baseline data shall include:

1. Demographics: age, sex, etiology of liver disease
2. Liver and renal function tests: bilirubin, AST, ALT, albumin, alkaline phosphatase, GGTP, BUN, creatinine, Na, INR, platelet count
3. Presence or absence of clinical ascites and encephalopathy\*
4. Serum alpha fetoprotein
5. MRI abdomen/pelvis
6. Chest CT
7. Performance status according to ECOG

Follow up data shall include:

- o ECOG Performance Status assessment
- o Standard laboratory blood draw for CBC, differential, electrolytes, BUN, liver function test, coagulation panel, and  $\alpha$ -fetoprotein biomarker
- o Adverse event reporting
- o Abdomen/pelvis MRI (6 weeks after treatment, 12 weeks after treatment and 3 months thereafter for a period of 2 years)
- o Chest CT scan (6 weeks after treatment, 12 weeks after treatment and 3 months thereafter for a period of 2 years)

# The Impact of $^{90}\text{Yttrium}$ (Y90) Radiation Segmentectomy on Unresectable Hepatocellular Carcinoma

## Progression:

Definition of tumor progression is defined as:

- Radiological progression as defined by mRECIST
- Development of extra-hepatic disease beyond the limits defined in the eligibility criteria
- ECOG Performance Status  $\geq 2$

ECOG Performance Status

### Score Characteristics

0 Asymptomatic and fully active

1 Symptomatic; fully ambulatory; restricted in physically strenuous activity

2 Symptomatic; ambulatory; capable of self-care; more than 50% of waking hours are spent out of bed.

3 Symptomatic; limited self-care; more than 50% of waking hours are spent in bed

4 Completely disabled; no self-care; bedridden

\* Grades of Encephalopathy

Grade 1      Inverted sleep pattern; forgetfulness, agitation, irritability, apraxia

Grade 2      Lethargy; Disorientation for time or place, Subtle personality change; Asterixis, ataxia

Grade 3      Somnolence but rousability; Disorientation as regards place; Asterixis, hyperactive reflexes, Babinski signs, muscle rigidity

Grade 4      Coma (unresponsive to verbal or noxious stimuli)

## MRI protocol:

Precontrast sequences (T1 in- and out-of-phase, T2 fat saturated, T2 HASTE, diffusion using 3 b-values: 50-400-800, T2\*) and dynamic pre- and postcontrast 3D T1-weighted imaging using Gadoxetic acid contrast (Eovist, Bayer) at the arterial, portal venous, late venous, and hepatobiliary phases. GFR will be measured prior to examination.

In addition to mRECIST, radiological parameters to be measured will include:

1. Maximum tumor diameter
2. Signal intensity enhancement in tumors at the arterial and portal venous phases.
3. Degree of tumor necrosis using image subtraction (27)
4. Tumor ADC: in whole tumor and viable tumor components, we will measure mean ADC  $\pm$  SD.
5. Liver uptake: we will measure contrast uptake on the hepatobiliary phase 20 min post contrast injection in the peritumoral area to assess for hepatocyte damage.

